Grade 3 (>2.0 - 5.0 x ULN with signs or symptoms; >5.0 x ULN and asymptomatic)	
Omit study treatment until resolved to ≤ grade 1, then resume nazartinib at the same dose level:
 
 
• If resolved in ≤ 14 days, resume capmatinib at the same dose level
 
• If resolved in > 14 days, resume capmatinib at ↓ 1 dose level
 
• If recurrence of grade 3 toxicity during nazartinib monotherapy, omit study treatment until resolved to ≤ grade 2, then ↓ 1 dose level nazartinib
 
• If no recurrence of grade 3 toxicity after 7 days of nazartinib monotherapy at ↓ 1 dose level, resume capmatinib at ↓ 1 dose level
 

Grade 4 (>5.0 x ULN and with signs or symptoms)	Permanently discontinue capmatinib and omit nazartinib until resolved to grade ≤ 2, then maintain dose level of nazartinib. Monitor for recurrence of grade 3 toxicity after 7 days or sooner if clinically indicated

Note: Perform diagnostic procedures (e.g., abdominal CT scan or ultrasound) to exclude pancreatic pathology. Withhold study treatment for acute onset of new or progressive unexplained abdominal symptoms, such as severe pain or vomiting; if diagnosed with pancreatitis ≥ grade 3 permanently discontinue from capmatinib treatment.
	
HBV and HCV reactivation	
Refer to Table 6-10 , Table 6-11 and Table 6-12 , and Section 6.3.2 for details.	
CARDIAC	
Electrocardiogram QT corrected (QTc) interval prolonged	
Grade 3 (QTc ≥ 501 ms on at least two separate ECGs)	
Omit study treatment until resolved to ≤ grade 1 then:
 
 
• If resolved in ≤ 7 days, resume capmatinib at same dose level and nazartinib at ↓ 1 dose level
 
• If resolved in > 7 days, resume capmatinib and nazartinib at ↓ 1 dose level
 

Grade 4 ([QT/QTc ≥ 501 or > 60 ms change	Permanently discontinue nazartinib and capmatinib.

Worst toxicity CTCAEa Grade (value)	Recommendation
from baseline] and [Torsades de pointes or polymorphic ventricular tachycardia, or signs/symptoms of serious arrhythmia])	Obtain local cardiologist (or qualified specialist) consultation and repeat cardiac monitoring as indicated until the QTcF returns to <481 ms.
VASCULAR DISORDERS	

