Grade 3 (> 3.0 - 10.0 x ULN)	Omit dose until resolved to ≤ grade 1, then 
 
• If fully resolved in ≤ 7 days, resume at ↓ 1 dose level
 
• If fully resolved in > 7 days, permanently discontinue capmatinib treatment
 

Grade 4 (> 10.0 x ULN)	Mandatory: Permanently discontinue capmatinib treatment
Isolated AST or ALT elevation	
Grade 1 (> ULN - 3 x ULN)	Maintain dose level
Grade 2 (> 3.0 - 5.0 x ULN)	Maintain dose level
Grade 3 (> 5.0 - 20.0 x ULN)	Omit dose until resolved to ≤ grade 1 (or ≤ grade 2 if grade 2 elevation at baseline) then 
 
• If fully resolved in ≤ 7 days, then resume at the same dose level
 
• If fully resolved in > 7 days, resume at ↓ 1 dose level
 

Grade 4 (> 20.0 x ULN)	Mandatory: Permanently discontinue capmatinib treatment
Combined elevations of AST or ALT and Total Bilirubinb,c,d	
For participants with normal baseline ALT and AST and total bilirubin value: AST or ALT > 3.0 x ULN combined with total bilirubin > 2.0 x ULN without evidence of cholestasis or hemolysis OR For participants with elevated baseline AST or ALT or total bilirubin value:	Mandatory: Permanently discontinue capmatinib treatment

Worst toxicity CTCAE Gradea during a cycle of therapy	Recommendation
[AST or ALT > 3 x baseline] OR [AST or ALT > 8.0 x ULN], whichever is lower, combined with [total bilirubin > 2 x baseline AND > 2.0 x ULN] without evidence of cholestasis or hemolysis	
METABOLIC	
Amylase and/or lipase elevation	
Grade 1 (> ULN - 1.5 x ULN)	Maintain dose level
Grade 2 (> 1.5 - 2.0 x ULN; > 2.0 - 5.0 x ULN and asymptomatic)	Maintain dose level
Grade 3 (> 2.0 - 5.0 x ULN with signs or symptoms; > 5.0 x ULN and asymptomatic)	Omit the dose until resolved to ≤ grade 1, then 
 
• If fully resolved in ≤ 14 days, resume at the same dose level
 
• If fully resolved in > 14 days, then resume at ↓ 1 dose level
 

Grade 4 (> 5.0 x ULN with signs or symptoms)	Permanently discontinue capmatinib treatment
CARDIAC	
Electrocardiogram QT corrected (QTc) interval prolonged	
Grade 1 (QTcF 450-480 ms) Grade 2 (QTcF 481-500 ms)	Maintain dose level

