For participants with normal baseline ALT, AST and total bilirubin value: AST or ALT >3.0 x ULN combined with total bilirubin >2.0 x ULN without evidence of cholestasis e OR For participants with elevated baseline AST or ALT or total bilirubin value: [AST or ALT >2x baseline AND > 3.0 x ULN] OR [AST or ALT > 8.0 x ULN], whichever is lower, combined with [total bilirubin >2x baseline AND >2.0 x ULN]	Mandatory: Permanently discontinue nazartinib. Repeat as soon as possible, preferably within 48 hours from awareness of the abnormal results, then with weekly monitoring of LFTs b ), or more frequently if clinically indicated, until AST, ALT, or bilirubin have resolved to baseline or stabilization over 4 weeks.
METABOLICh	
Asymptomatic amylase and/or lipase elevation	
Grade 1 (>ULN - 1.5 x ULN)	May maintain dose level
Grade 2 (>1.5 - 2.0 x ULN)	May maintain dose level
Grade 3 (>2.0 - 5.0 x ULN)	Recommendation: omit dose until resolved to Grade ≤ 2, then: If fully resolved in ≤ 14 days, then resume at same dose level If fully resolved in >14 days, then resume at ↓ 1 dose level
Grade 4 (>5.0 x ULN)	Recommendation: Omit dose and discontinue nazartinib
Note: withhold nazartinib for acute onset of new or progressive unexplained abdominal symptoms, such as severe pain or vomiting; perform diagnostic procedures (e.g., abdominal CT scan or ultrasound) to exclude pancreatic pathology.	
HBV and HCV reactivation Refer to Table 6-10 , Table 6-11 and Table 6-12 , and Section 6.3.2 for details.	
CARDIAC	
Electrocardiogram QT corrected (QTc) interval prolonged	
Grade 1 (QTc 450-480 ms)	May maintain dose level
Grade 2 (QTc 481-500 ms)	May maintain dose level
Grade 3 (QTc ≥ 501 ms on at least two separate ECGs)	Recommendation: omit dose until QTc is less than 481 ms and then resume at ↓ 1 dose level 

Perform an analysis of serum potassium, and if below lower limit of normal, correct with supplements to within normal limits. Repeat ECG in 24 hours, or less, as clinically indicated; continue monitoring as clinically indicated until QTc <481 ms

Worst toxicity CTCAEa Grade (value) during a cycle of therapy	Recommendations

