
e "Cholestasis" defined as: ALP elevation (>2xULN and R value< 2) in participants without bone metastasis, or elevation of ALP liver fraction in participants with bone metastasis
 
Note: The R value is calculated by dividing the ALT by the ALP, using multiples of the ULN for both values. It denotes the relative pattern of ALT and/or ALP elevation is due to cholestatic or hepatocellular liver injury
 
f If combined elevations of AST or ALT and total bilirubin do not meet the defined thresholds, please follow the instructions for isolated elevation of total bilirubin and isolated elevation of AST/ALT, and take a conservative action based on the degree of the elevations (e.g., discontinue treatment at the situation when omit dose is needed for one parameter and discontinue treatment is required for another parameter). After all elevations resolve to the defined thresholds that allow treatment re-initiation, re-start the treatment either at the same dose or at one dose lower if meeting a criterion for dose reduction
 
g Note: If total bilirubin > 3.0 x ULN is due to the indirect (non-conjugated) component only, and hemolysis as the etiology has been ruled out as per institutional guidelines (e.g., review of peripheral blood smear and haptoglobin determination), then ↓ 1 dose level and continue treatment at the discretion of the investigator.
 
h A CT scan or other imaging study to assess the pancreas, liver, and gallbladder must be performed within 1 week of the first occurrence of any ≥ Grade 3 of amylase and/or lipase. If asymptomatic Grade 2 elevations of lipase and/or amylase occur again at the reduced dose, participants will be discontinued permanently from study treatment.
 
iAntidiarrheal medication is recommended at the first sign of abdominal cramping, loose stools or overt diarrhea.
	

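### Under one cited CTCAE version, Table 6-9 grades asymptomatic amylase/lipase above 2x ULN higher than Tables 6-7 and 6-8, so sites can get conflicting instructions on nazartinib

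*Protocol*

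**What the plan says.** Footnote a of each of Tables 6-7, 6-8 and 6-9 names CTCAE 5.0 as the grading scale.

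- **Table 6-9 (nazartinib alone).** The row covers asymptomatic amylase/lipase elevations only. Grade 2 is >1.5-2.0x ULN and the dose may be kept. The next band is "Grade 3 (>2.0 - 5.0 x ULN", for which the dose is omitted until Grade 2 or lower. Above 5.0x ULN is Grade 4, with the action "Recommendation: Omit dose and discontinue nazartinib".
- **Table 6-8 (capmatinib alone).** The bands are "Grade 2 (> 1.5 - 2.0 x ULN; > 2.0 - 5.0 x ULN and asymptomatic", with the dose maintained, and "Grade 3 (> 2.0 - 5.0 x ULN with signs or symptoms; > 5.0 x ULN and asymptomatic", with the dose omitted and then resumed.
- **Table 6-7 (combination).** It prints no Grade 1 or 2 row. Its third band is "Grade 3 (>2.0 - 5.0 x ULN with signs or symptoms; >5.0 x ULN and asymptomatic", with the action "Omit study treatment until resolved to ≤ grade 1, then resume nazartinib at the same dose level". Its Grade 4 row, for symptomatic values above 5x ULN, stops capmatinib permanently, holds nazartinib until Grade 2 or lower, and then keeps the nazartinib dose level.
- **Footnote h** stands under Tables 6-7 and 6-9. Imaging of the pancreas, liver and gallbladder "must be performed within 1 week of the first occurrence of any ≥ Grade 3 of amylase and/or lipase". It adds: "If asymptomatic Grade 2 elevations of lipase and/or amylase occur again at the reduced dose, participants will be discontinued permanently from study treatment".

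**The concern.** Different drugs may justify different actions for the same laboratory value. They do not justify different grades for that value when the tables cite the same grading version. Here the grade decides what happens in two places.

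The first is the hand-over from Table 6-7 to Table 6-9. Table 6-7's own pancreatic Grade 4 row can put a participant on nazartinib alone, and it sets the restart by grade. Table 6-9 then applies to that participant with a stricter meaning of the same grade.

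The second is footnote h. It sets mandatory imaging and a permanent stop by grade, with no x ULN figure, and it appears under two tables whose bands differ.

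At stake is whether sites omit or restart nazartinib, and whether they image, consistently for the same participant.

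**Working it through.** No sample size, power or error rate is involved, so the check is to grade the same asymptomatic values under each table.

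**Bands for asymptomatic values (x ULN)**

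- Table 6-9: Grade 1 up to 1.5; Grade 2 >1.5-2.0; Grade 3 >2.0-5.0; Grade 4 >5.0.
- Table 6-8: Grade 1 up to 1.5; Grade 2 >1.5-5.0 (the two asymptomatic parts joined); Grade 3 >5.0.
- Table 6-7: Grade 3 >5.0. Between 2.0 and 5.0 only values with symptoms are Grade 3, so an asymptomatic value there is Grade 2 or lower by exclusion.

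| Asymptomatic value (x ULN) | Table 6-7 | Table 6-8 | Table 6-9 |
|---|---|---|---|
| 1.2 | below Grade 3 | 1 | 1 |
| 1.8 | below Grade 3 | 2 | 2 |
| 3 | below Grade 3 | 2 | 3 |
| 4.9 | below Grade 3 | 2 | 3 |
| 6 | 3 | 3 | 4 |

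Tables 6-8 and 6-9 agree up to 2x ULN. Above 2x ULN, Table 6-9 is one grade higher than Table 6-8. Above 5x ULN it is also one grade higher than Table 6-7.

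**Hand-over case.** Take a Group 5 participant on the combination with a symptomatic value above 5x ULN.

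1. Table 6-7, Grade 4: capmatinib is permanently stopped and nazartinib is held until Grade 2 or lower.
2. Symptoms clear and the value falls to 3x ULN. Table 6-7's Grade 3 row does not include an asymptomatic 3x ULN, so the restart condition is met.
3. The participant is now on nazartinib alone, which is the scope of Table 6-9. There 3x ULN is Grade 3, and the action is to omit until Grade 2 or lower, that is, 2.0x ULN or less.

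The asymptomatic restart limit is therefore 5.0x ULN by Table 6-7 and 2.0x ULN by Table 6-9. Any value between the two gets opposite instructions.

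**Imaging case.** At asymptomatic 3x ULN, footnote h's Grade 3 trigger is met under Table 6-9. It is not met under Table 6-7, because neither the Grade 3 nor the Grade 4 row there contains that value.

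**The case against.** The strongest defence is that each row of Table 6-9 prints its x ULN band. Within that table a site can act on the number and ignore the label. That is right for the row actions. It does not cover footnote h or Table 6-7's restart condition, both of which give a bare grade.

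Four stronger readings are tempting, and the documents do not support them.

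- **That Table 6-9 is the table in error.** Its bands match those of the dose-limiting toxicity table (Table 6-4), whose footnote cites CTCAE 4.03. That suggests carry-over from an older scale, but it is only an inference. The grading criteria are not reproduced in the protocol.
- **That the different action at 6x ULN is itself a mistake.** Table 6-7 resumes nazartinib and Table 6-9 recommends stopping it. But Table 6-7 makes capmatinib the first drug to adjust, while in Table 6-9 nazartinib is the only study drug left. Stricter handling there can be deliberate.
- **That footnote h's permanent stop for recurrent Grade 2 is much wider under one table than the other.** Table 6-7 prints no Grade 2 band, and Table 6-8, which does, carries no such footnote. The text alone gives no range for Table 6-7.
- **That imaging is absent at 3x ULN on the combination.** Table 6-7 has a separate Note, with no grade attached, calling for diagnostic procedures to exclude pancreatic pathology. Footnote h's one-week deadline still differs between the tables.

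The reach is also small. At Amendment 07 no Phase Ib or Group 1 to 4 participant was on treatment. Section 6.3.1 limits single-drug continuation to exceptional cases discussed with the sponsor and allows case-by-case exceptions. Table 6-9's pancreatic row actions are recommendations. All of this stands and keeps the point minor.

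**Conclusion.** The inconsistency is real and minor. Three tables cite one grading version, yet Table 6-9 grades asymptomatic amylase/lipase one grade higher than Table 6-8 above 2x ULN, and one grade higher than Table 6-7 above 5x ULN. At least one table misapplies its scale.

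The practical effect is twofold. Instructions on restarting nazartinib conflict for asymptomatic values above 2.0 and up to 5.0x ULN after a Table 6-7 Grade 4 event. The Grade 3 imaging trigger also covers different values under Tables 6-7 and 6-9. ORR, the interim analysis and sample size do not change.

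This rests on two readings: that Grade 2 or lower in Table 6-7 takes its meaning from that table's own Grade 3 row, and that Table 6-9 applies once capmatinib has been permanently stopped.

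A reader comparing these tables might also infer a fault in the combined-liver stop. For an elevated baseline, Tables 6-7 and 6-8 use a multiple of baseline AST/ALT without the >3x ULN floor in Tables 6-4 and 6-9. That is not part of this finding. The missing floor lowers the limit only when the enzyme that rises was below ULN at baseline. Bilirubin must also exceed 2x baseline and 2x ULN, and an earlier stop is conservative. The sponsor may wish to check it.

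**What to change.** In one edit to Section 6.3.1:

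1. Check the amylase/lipase bands against CTCAE 5.0 and print one set in Tables 6-7, 6-8 and 6-9.
2. If stricter action is intended for nazartinib alone, keep it and state it by value, for example omit at asymptomatic >2-5x ULN. Otherwise, if the Table 6-8 bands are adopted, that range would move from omit to the Grade 2 action in Table 6-9, which allows the dose to be kept. That would loosen a safety rule.
3. State the nazartinib restart threshold in Table 6-7's Grade 4 row in x ULN, and make it agree with Table 6-9.
4. State both triggers in footnote h (imaging, and the permanent stop on recurrence) in x ULN under Tables 6-7 and 6-9. Re-banding then cannot change what they cover without anyone noticing.

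The cost is a table and footnote correction plus a clarification to sites. No analysis, sample size or interim rule changes.

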### 6.3.2 Guidelines for screening, monitoring and management of HBV / HCV reactivation

#### HBV screening tests, on study monitoring, and management of HBV reactivation
